Research Project Title

Assessing gestational age in first trimester pregnancies: A comparison of a new handheld wireless transabdominal ultrasound to a portable transabdominal ultrasound.

Research Question

This research project is designed to determine the equivalence of a handheld wireless (Clarius C3) transabdominal ultrasound to the current portable ultrasound with transabdominal and transvaginal capabilities (Zonare ZS3) when used to date first trimester pregnancies.

Background

There have been several new recommendations in the SOGC encouraging the provision of first trimester pregnancy ultrasound.

In the June 2018 SOGC Clinical Practice Guideline No 360-Induced Abortion: Surgical Abortion and Second Trimester Medical Methods, the authors write, “Ultrasound should be performed prior to induced abortion to confirm gestational age and aid in operative planning (Strong recommendation. Level of evidence: Low)”. In the SOGC Clinical Practice Guidelines on Medical Abortion published in 2016, they recommend that “women with significant risk factors, signs, or symptoms of ectopic pregnancy should have a pretreatment ultrasound before medical abortion”, but they does not require it to be performed. In patients who receive medical abortion (Mifepristone 200 mg orally followed by misoprostol 800 mcg buccally 24 to 48 hours) under 9 weeks’ gestation, the product monograph states that “ultrasound shall be performed before medical abortion”. It is the current standard at the sites that perform medical abortion in Manitoba (Women’s Hospital, Winnipeg Health Clinic Portage and Brandon Hospital) that an ultrasound is performed prior to medical abortion to confirm an intrauterine pregnancy. In March 2019, the SOGC developed a Clinical Practice Guideline on the Use of First Trimester Ultrasound. They recommended the following: “First trimester ultrasound is recommended to date a pregnancy (ideally at 7 to 12 weeks).”

The cost of wireless portable ultrasounds that connect with a tablet computer or smart phone has made it more accessible for the average obstetrician/gynecologist going into practice. Canadian residents training in Obstetrics and Gynecology are now required to complete a month of training in ultrasound in their PGY1 year. If an inexpensive handheld ultrasound machine can be used to appropriately date a first trimester pregnancy, it would allow for the average obstetrician/gynecologist to appropriately date a pregnancy, regardless of their location. This would be highly valued in locations where ultrasound access by radiologists is not easily accessible.

In the SOGC practice guidelines Determination of Gestational Age (GA) by Ultrasound published February 2014, a mean sac diameter (MSD) is first used to date pregnancy using a transvaginal ultrasound when it is 2-3 mm or 32 to 33 days. The growth of the MSD is approximately 1 mm per day. Mean sac diameter becomes less reliable when it exceeds 14 mm or an embryo can be identified. A yolk sac or embryo seen inside the gestational sac in an intrauterine location provides confirmation that the pregnancy is definitely in the uterus. This makes an ectopic pregnancy extremely unlikely. The yolk sac usually becomes visible between 5 to 6 weeks GA. The embryo is usually seen after 6 weeks' GA. Crown rump length provides the most accurate estimate of gestational age when the embryo is clearly seen and it is reported to be accurate within 3-8 days. The SOGC recommend that crown rump length be used up to 84 mm in size (approximately 12 weeks and 4 days with Hadlock criteria), and the biparietal diameter be used for measurements greater than 84 mm. These criteria will be used to determine gestational age for the study.

Objective:

The objective of this study is to assess equivalency of the transabdominal Clarius handheld wifi C3 ultrasound (which uses Bluetooth to locate the iPad Mini 5 and then uses wifi direct to show the images) to the current standard of care in Women's Hospital outpatient department the portable Zonare ZS3 in patients presenting in the first trimester of pregnancy.

Research Design and Methodology

This is a prospective clinical study in which first trimester participants who are presenting to discuss termination of pregnancy, will consent to have an additional transabdominal ultrasound with the Clarius C3 immediately prior to their standard ultrasound which is performed to date their pregnancy. Participants who are presenting for medical abortion have been prescreened to be estimated to be less than 9 weeks GA. Participants who are being seen prior to surgical abortion will have been screened by nurses based on their last menstrual period or estimated time of conception to estimate their gestational age. Potential participants estimated to be less than 13 weeks GA, will be approached to see if they are interested in participating in the study before they are seen by their health care provider. The name, date of approach, and reason for decline of potential participants who refuse to participate will be documented. If agreeable, the participant will complete consent with a study nurse or medical student for the additional ultrasound.

Participants will then receive the 2 ultrasounds by the same health care provider with the Clarius C3 ultrasound first, then the standard care ultrasound. Occasionally, there may be a different provider doing the Clarius C3 ultrasound when the patient consents.

Participants will receive standard care for medical or surgical abortion. The following information will be documented from their chart:

Height and weight, age, Obstetrical history (Gravida, para, number cesareans, ectopic pregnancies, spontaneous abortions, therapeutic abortions). If they do not have a

documented intrauterine pregnancy, the standard questions to rule out possibility of ectopic pregnancy will be determined, and any positive answers will be documented in the chart. Anyone without a documented intrauterine pregnancy (no gestational sac or a gestational sac with no definite crown rump length or yolk sac) will be followed until a final outcome is determined or they are lost to follow up. When the patient has a pregnancy of unknown location (no evidence of a pregnancy inside or outside of the uterus, their data will not be used to compare the two ultrasounds but future outcome will be recorded.

The final outcome of their pregnancy and any complications will be determined within the next 6 weeks with the following potential outcomes:

completed medical abortion, completed surgical abortion (possibly following failed medical abortion), lost to follow up, continuing pregnancy, or ectopic pregnancy.

If a participant is determined to be over 13 weeks GA, they will receive a dating ultrasound with the Clarius C3 ultrasound using biparietal diameter as appropriate but it will not be included in the final study measurements.

For each participant, ultrasound reports and data from the "Research Participant Data Collection Form" will have a unique code and all information stored on a password-protected SPSS document on a locked desktop computer in the Research Office WS021 which is locked.

Sample Size

Sample size was estimated based on a one sided McNemar's test, 15% clinically significant difference (estimating 60% of subjects would allow a transabdominal ultrasound to see a gestational sac and a yolk sac with the Zonare ZS3 and 45% with the Clarius C3) at a power of .8 and alpha value of 0.05. This would require 131 participants to be recruited for the study.

Statistical Analysis

McNemar's test would be used to determine the ability of the transabdominal ultrasounds to measure the presence or absence of an intrauterine pregnancy. A paired t-test would be used to compare gestational sac measurements or crown rump lengths between the two ultrasound machines.

Inclusion Criteria

1. Presenting requesting medical or surgical abortion
2. Estimated to be under 13 weeks gestational age based on last menstrual period or time of conception, or nurses best estimate.
3. Able to provide informed consent with adult supervision of a minor or with an interpreter present

Exclusion Criteria

1. Unable to provide informed consent

Timeline

We anticipate data collection to occur over a 9-month period.

Budget

Data collection by the participating physicians will be on a volunteer basis. A medical student volunteer will not be paid for the procedure. Physicians who perform ultrasound for medical and surgical abortion will be reimbursed by Manitoba Health for their procedure with no additional funding for participation in the study. The study nurses involved in recruiting, consenting and collecting data will be paid by the Department of Obstetrics and Gynecology.

Conflict of interest

There is no conflict of interest identified in this study.

Discussion of Ethics*Informed consent*

Potential participants will be identified by nursing or physician. A volunteer medical student or research nurse will approach the patient to request consent.

Potential Benefits and Harms

The additional ultrasound may be associated with minimal physical discomfort due to pressure on their bladder. There is minimal risk to a developing pregnancy due to ultrasound. Participants will be chosen among patients requesting termination of pregnancy.

Alternative Procedures

The patient may choose to receive usual care and not receive a second ultrasound.

Protection of privacy and harm reduction

- Participation is strictly voluntary
- All personal information contained on the consent forms will be kept in a locked cabinet in the Research Office WS021 which itself is locked. These paper records will be destroyed via shredding at the end of the study.
- Ultrasound images obtained from patients will be initially stored on Clarius cloud using anonymized data and printed out to be placed in the study chart
- Information gathered from patient charts, and ultrasound image reports will be identified by a unique code and stored on a password-protected SPSS Document stored on a locked Desktop computer in the locked Research Office WS021. These files will be destroyed using the permanent deletion function on the computer if no further secondary research is planned within seven years.

Dissemination of information

Final results will be presented locally and also at a national or international forum. The data may be used to design future studies with regard to performing ultrasound in remote locations in Manitoba or Nunavut.

References

Butt K, Lim K et al. Determination of Gestational Age by Ultrasound. J Obstet Gynaecol Can 2014;36(2):171-181

Van den Hof M, Smithies M, Nevo O, et al. No. 375- Clinical Practice Guideline on the Use of First Trimester Ultrasound. J Obstet Gynaecol Can 2019;41(3):388-395

Costescu D, Guilbert E et al. No 360-Induced Abortion: Surgical Abortion and Second Trimester Medical Methods. J Obstet Gynaecol Can 2018;40(6):750-783

Van den Hof M, No 359-Obstetric Ultrasound Biological Effects and Safety. J Obstet Gynaecol Can. 2018;40(5):627-632

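### The only planned dating comparison is a test of mean size, which cannot show whether the two machines agree on gestational age for individuals, including at the 9-week prescreening limit

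*Combined protocol and SAP*

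**What the plan says.** The Research Question and Objective of the combined protocol and SAP set an equivalence aim for the Clarius C3 against the Zonare ZS3 "when used to date first trimester pregnancies". Neither section gives an equivalence margin.

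Statistical Analysis lists two comparisons. The first is on visibility: "McNemar's test would be used to determine the ability of the transabdominal ultrasounds to measure the presence or absence of an intrauterine pregnancy". The second is on size: "A paired t-test would be used to compare gestational sac measurements or crown rump lengths between the two ultrasound machines". The section mentions no gestational age in days, no limits of agreement and no classification by gestational age.

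Research Design and Methodology describes the standard scan as the one that dates the pregnancy, and then says of one of the two recruitment streams: "Participants who are presenting for medical abortion have been prescreened to be estimated to be less than 9 weeks GA". Background also describes medical abortion as given under 9 weeks, and says of the Manitoba sites that "an ultrasound is performed prior to medical abortion to confirm an intrauterine pregnancy". The end of Background sets out the mean sac diameter, crown rump length and biparietal diameter criteria by which gestational age is to be determined in the study.

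**The concern.** Equivalence for dating is a statement about agreement: for the same pregnancy, the two machines should give nearly the same age. A paired t-test examines only whether the average difference is zero. Positive and negative differences cancel, so large individual disagreements can leave the mean, and hence the test, undisturbed. The McNemar table does not fill the gap, because it cross-classifies seen against not seen.

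The 9-week limit makes the gap concrete. Two readings of one pregnancy can fall on opposite sides of a limit the protocol itself uses, and nothing planned would record how often this happens or in which direction. The spread of differences in days helps, but does not by itself give the count, which also depends on how many participants lie near 63 days.

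There is also a loss of data. A pair with a sac measurement on one machine and a crown rump length on the other has no like-for-like difference in millimetres, and a participant dated by only one machine has none at all. Such participants could drop out of the t-test without being reported.

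At stake is the conclusion. The study could report no significant difference in size and treat that as equivalence for dating.

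**Working it through.** **Inputs from the documents.** Limit of 9 weeks = 9 × 7 = 63 days (Research Design and Methodology); 131 participants, 60% against 45% visibility, one-sided alpha 0.05, power 0.80 (Sample Size); crown rump length accurate within 3 to 8 days (Background).

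**Assumptions, not in the documents.** No mean difference between machines; normal errors; the 3 to 8 days read as a 95% range for each machine; true age uniform over 35 to 91 days (width 56); correlation between the two machines' errors of 0 or 0.8.

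**1. The plan's own figure.** The basis is "Sample size was estimated based on a one sided McNemar's test, 15% clinically significant difference". The discordant share is not stated. Taking the two readings as independent, it is 0.60 × 0.55 + 0.40 × 0.45 = 0.51. Then N = (1.645 + 0.842)² × (0.51 − 0.15²) / 0.15² = 133.96, or 134, within 3% of 131. The figure is reproduced, but it sizes a visibility comparison and says nothing about dating agreement.

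**2. What the t-test can show.** With zero mean difference, a test at the 5% level is non-significant 95% of the time whatever the spread. This holds by construction; simulated runs gave 94% to 96%. An extreme illustration: 65 pairs at +7 days, 65 at −7 and one at 0 give a mean of 0, an SD of 7.0 days, t = 0 and p = 1.0.

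**3. Share of pairs split by 63 days.** For a pair differing by D days, the chance that 63 falls between the two readings is about |D|/56. Averaged over pairs this is 0.798 × SD(D) / 56, where SD(D) = (accuracy / 1.96) × √(2(1 − correlation)). Counts are shown for 131 pairs and for 59 (0.45 × 131). The 59 takes the Clarius visibility rate as the share dated by both machines, which is itself an assumption.

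| Correlation | Accuracy (days) | SD(D), days | 95% range of D, days | Split | Of 131 | Of 59 |
|---|---|---|---|---|---|---|
| 0.8 | 3 | 0.97 | ±1.9 | 1.4% | 1.8 | 0.8 |
| 0.8 | 8 | 2.58 | ±5.1 | 3.7% | 4.8 | 2.2 |
| 0 | 3 | 2.16 | ±4.2 | 3.1% | 4.0 | 1.8 |
| 0 | 8 | 5.77 | ±11.3 | 8.2% | 10.8 | 4.9 |

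With no bias, half of each count has the Clarius under 9 weeks and the Zonare at 9 weeks or over. The t-test behaves the same way in all four rows, although the individual differences range from under 2 days to over 11.

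**4. Sensitivity to the age spread.** Ages concentrated nearer the limit raise the count. With age normal (mean 56, SD 12 days) and SD(D) = 5.66 days, about 16 of 131 (12%) are split; with age uniform over 42 to 63 days and the same SD, about 14.

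**5. Precision of a reported count.** Exact 95% intervals at n = 131: 3 split pairs, 2.3% (0.5% to 6.5%); 7 pairs, 5.3% (2.2% to 10.7%); 13 pairs, 9.9% (5.4% to 16.4%).

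**The case against.** A reader might infer that splits at 9 weeks are decision-changing. The documents do not support that. They use 9 weeks as a prescreening estimate, and no section says what follows if the scan dates at 9 weeks or more. Background gives the local purpose of the scan before medical abortion as confirming an intrauterine pregnancy, which the McNemar test addresses. The guideline sentence there about confirming gestational age comes from a guideline on surgical abortion and second trimester medical methods. Nor is 9 weeks the only limit in play: 13 weeks governs eligibility and which measurements count. Participants also receive the standard scan, so the gap does not touch care within the study. All of this stands.

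The size is open to attack too. The two scans are of the same embryo at one visit, usually by the same provider, so part of the 3 to 8 days is shared and cancels in the difference. Independent errors therefore probably overstate disagreement, which is why the 0.8 case is shown. The counts out of 131 include surgical participants, for whom the documents attach nothing to 9 weeks, and the size of the medical stream is not given. These points stand as well.

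Finally, the wider defect is that a test of the mean serves an equivalence aim with no margin, and a 9-week table is only one way to display agreement. That is fair, and it is why the table belongs beside the spread of paired differences and does not replace it. It does not remove the gap: the stated aim is dating, the protocol says the standard scan dates the pregnancy, and nothing planned shows individual agreement at any gestational age.

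**Conclusion.** The concern holds in a limited form. The single planned dating analysis cannot support a statement of equivalence for dating, because a non-significant mean difference is compatible with individual disagreement of any size, including on which side of 9 weeks a pregnancy falls.

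How many pairs would be split cannot be derived from the documents, which give no between-machine SD and no age distribution. Under zero bias and an even 35 to 91 day spread, the range is 1.4% to 8.2%, about 2 to 11 of 131, or about 1 to 5 of 59. The lower part of each range rests on an assumed error correlation of 0.8 and the upper part on independence. The count within the medical abortion stream is unknown. The defect itself does not depend on these figures, since the t-test is uninformative about agreement at any spread.

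**What to change.** In Statistical Analysis:

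- Derive gestational age in days from each machine, using the criteria at the end of Background.
- Report the paired mean difference together with the spread of the paired differences in days.
- Cross-tabulate Clarius against Zonare as under 9 weeks, 9 weeks or over, or not datable, overall and in the medical abortion stream.
- Report the two discordant cells (Clarius under and Zonare at or over 9 weeks, and the reverse) separately, as counts and percentages with exact 95% confidence intervals and a stated denominator.
- Keep participants dated by the Zonare but not by the Clarius in the table.
- State that a conclusion of dating equivalence will not rest on a non-significant t-test alone.

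The cost is one extra table from measurements the study already takes, with no new procedure and no change to the sample size. The intervals will be fairly wide, more so in the medical stream. This is an analysis of agreement at a limit the protocol already uses, and it proposes no clinical rule.

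### The Clarius is always scanned first, normally by the same provider, so device and scan order cannot be separated and measurement agreement may be inflated; a few recording steps would limit part of this cheaply.

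*Combined protocol and SAP*

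**What the plan says.** Research Design and Methodology gives the order twice. Participants consent to an "additional transabdominal ultrasound with the Clarius C3 immediately prior to their standard ultrasound", and then: "Participants will then receive the 2 ultrasounds by the same health care provider with the Clarius C3 ultrasound first, then the standard care ultrasound". There is one exception on the operator: "Occasionally, there may be a different provider doing the Clarius C3 ultrasound when the patient consents". No exception is given on the order.

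The protocol does not describe masking the second reading to the first, fixing the first reading before the second scan, or varying the order. That the provider is unmasked is my inference, but someone who has just done the first scan knows its result.

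The Research Question says the project is "designed to determine the equivalence of a handheld wireless (Clarius C3) transabdominal ultrasound". Under Statistical Analysis, "McNemar's test would be used to determine the ability of the transabdominal ultrasounds to measure the presence or absence of an intrauterine pregnancy", and a paired t-test compares sac and crown-rump measurements. Neither analysis has a term for order or operator. Under Sample Size, "Sample size was estimated based on a one sided McNemar's test, 15% clinically significant difference".

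**The concern.** Every Clarius reading is a first reading and every Zonare reading is a second one. Any difference between the machines is then the device effect plus whatever scanning second does. In the occasional two-provider pairs, the operator changes with the device as well.

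The consequence differs by endpoint.

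- **Measurements.** A provider who has just placed calipers on the Clarius image may be drawn toward that value on the Zonare. This makes the machines look more alike than they are, which is the wrong direction for an equivalence claim. Dating is the purpose of the study, so this is the more important path.
- **Detection.** Having located the sac once could help the second scan, while having failed to see it could reduce the effort on the second transabdominal look. The two pull in opposite directions.

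**Working it through.** **Can device and order be separated?** Write each reading as intercept + device + order, with two readings per participant. Under the protocol the order indicator equals the device indicator in every row, so the design matrix has rank 2 of 3. Varying the order would raise the rank to 3. Locking the first reading or recording the operator leaves it at 2.

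**The plan's own figure.** Inputs from Sample Size: 60% and 45% detection (difference 0.15), one-sided alpha 0.05, power 0.80, N = 131. The discordant proportion d is not stated. With independent readings, d = 0.60 × 0.55 + 0.40 × 0.45 = 0.51.

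- Unpooled variance: (0.51 − 0.0225) × (1.645 + 0.842)² / 0.0225 ≈ 134, within 3% of 131.
- Usual McNemar formula, (1.645√d + 0.842√(d − 0.0225))² / 0.0225: 138 at d = 0.51, and 131 at d ≈ 0.484.

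So 131 is reproduced approximately, and nothing below depends on reproducing it exactly.

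**Detection: illustration.** The documents give no order effect, so the shifts here are assumptions. Let g be the shift in the Zonare-minus-Clarius difference caused by order alone. With truly equal devices, P(Zonare only) = (d + g)/2 and P(Clarius only) = (d − g)/2. Let b and c be the two discordant counts. I enumerated them for n = 131 and computed two probabilities:

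- *False Zonare advantage:* (b − c)/√(b + c) ≥ 1.645.
- *Similarity shown:* (b − c)/n + 1.645 × √((b + c) − (b − c)²/n)/n < 0.15. The plan states no similarity rule. This one is mine and borrows its 15 points.

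| Order shift g | False advantage, d = 0.30 | False advantage, d = 0.51 | Similarity shown, d = 0.30 | Similarity shown, d = 0.51 |
|---|---|---|---|---|
| −5 points | 0.4% | 0.7% | 99.4% | 94.2% |
| 0 | 5.0% | 5.0% | 93.1% | 77.8% |
| +1 point | 7.5% | 6.9% | 89.9% | 72.7% |
| +2 points | 10.9% | 9.3% | 85.7% | 67.2% |
| +5 points | 27.3% | 19.9% | 67.5% | 48.7% |

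The negative direction matters when the Clarius is truly worse. With a true 15-point deficit, similarity is wrongly shown 5.3% (d = 0.30) or 5.0% (d = 0.51) of the time. If order hides 5 of those points, the observed difference is 10 points and the rates become 28.4% and 20.2%.

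The 30% discordance is my choice and does not bound the effect: at 10%, a +5-point shift gives a false advantage in 59% of studies. The table also uses all 131 pairs, although the protocol drops unknown-location pregnancies and those over 13 weeks from the comparison.

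**Measurement: mechanism.** Let C and Z be the readings that would be taken independently. If the Zonare value is pulled a fraction w toward C, the recorded difference is C − [(1 − w)Z + wC] = (1 − w)(C − Z). If the Clarius value is later revised a fraction v toward the Zonare value, this becomes (1 − v)(1 − w)(C − Z). Assume a true mean difference of 1.0 mm and a reading SD of 2.0 mm per machine, so that 1.96 × 2.0 × √2 ≈ 5.5 mm:

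- no anchoring: mean 1.0 mm, half-width of limits of agreement 5.5 mm;
- w = 0.3: 0.70 mm and 3.9 mm;
- w = 0.3 and v = 0.3: 0.49 mm and 2.7 mm.

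Locking the Clarius value removes v only. It moves the third case back to the second, not to the first. In this simple model the mean and SD shrink together, so the t statistic is unchanged. What is flattered is the size of the difference, its confidence interval and the limits of agreement, which are what a judgement of equivalence would use.

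**The case against.** **The fixed order has a real merit.** The protocol does not say so, but with the Clarius first its operator has not yet seen the standard view, which may include transvaginal imaging. That matches the intended use, of which Background says: "This would be highly valued in locations where ultrasound access by radiologists is not easily accessible". Randomising the order would balance an additive order effect, but it would cost the Clarius that independence in half the participants and leave anchoring in place. This stands, and it is why I would not change the order.

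**A reader might infer that detection leans toward the Zonare, so that a finding of similarity is conservative.** The argument is that a provider has little reason to let a negative Clarius result carry over, because anyone without a documented intrauterine pregnancy "will be followed until a final outcome is determined or they are lost to follow up". The documents do not support this. The Research Question gives the Zonare transvaginal capability, so after a negative Clarius scan the pregnancy could be documented transvaginally with little effort on the Zonare transabdominal view. The follow-up rule does not protect that reading.

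**A reader might infer that locking the first reading and recording the operator would deal with anchoring.** They would not. Locking stops back-revision only, and recording the operator limits no bias by itself.

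**Some of this may already be in place.** The data collection form is named but not supplied, and may already have operator and timing fields. Under Protection of privacy and harm reduction, images are stored on the Clarius cloud and printed. Whether calipers are saved before the Zonare scan is not stated, so this does not show that the first reading is fixed; it may reduce how much the first step adds.

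**The detection figures do not size the measurement problem.** This is correct. They are illustrations for one endpoint, and the plan offers no basis for the other.

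**Conclusion.** The point holds as a limitation with an inexpensive partial remedy. As written, device and scan order are completely aliased in both planned comparisons, and the second measurement is normally taken with knowledge of the first. Measurement agreement can therefore be inflated in a study that aims to show equivalence. The direction of any order effect on detection is unknown, and neither effect can be sized from the documents. The figures above show only that shifts of a few points would matter at n = 131. They rest on assumed shifts, assumed discordance, a similarity rule that is mine, and assumed values for the anchoring example.

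A reader might go further and conclude that the design is invalid or that the order must be randomised. The documents do not support that: Clarius-first keeps the new device's reading independent.

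**What to change.** Keep the Clarius first and add four things by short amendment, to be done at the visit because they may not be recoverable afterwards:

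1. Record the Clarius transabdominal seen/not-seen result and save its caliper values before the Zonare is used, with no later revision. This stops back-revision only.
2. Where the machine allows, hide the Zonare numeric caliper readout until its image is saved. This is the step that acts on drift of the Zonare value toward the Clarius value.
3. Record the Zonare transabdominal seen/not-seen result before any transvaginal view, and the operator of each scan, so that two-provider pairs can be described.
4. State in the conclusion that device and order are not separable, that measurement agreement may be inflated, and that the direction of any detection bias is unknown.

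Cost: a small workflow change and a few form fields, some of which may already exist. There are no extra scans or staff, and N stays at 131. Limits: the provider still knows the first seen/not-seen result, hiding the readout depends on machine settings the documents do not describe, and the two-provider subset will be small.

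### The aim is equivalence, but both planned tests look only for a difference, and no margin, interval rule or agreement analysis is set

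*Combined protocol and SAP*

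**What the plan says.** The Research Question section states: "This research project is designed to determine the equivalence of a handheld wireless (Clarius C3) transabdominal ultrasound" to the portable Zonare ZS3, "when used to date first trimester pregnancies". The Objective section repeats it: "The objective of this study is to assess equivalency of the transabdominal Clarius handheld wifi C3 ultrasound" to the machine now in use.

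The Statistical Analysis section has two sentences. The first reads "McNemar's test would be used to determine the ability of the transabdominal ultrasounds to measure the presence or absence of an intrauterine pregnancy". The second plans a paired t-test of sac measurements or crown rump lengths between machines.

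The Sample Size section arrives at 131 participants from a one-sided McNemar test with power 0.8 and alpha 0.05. It expects a sac and yolk sac to be visible in 60% with the Zonare and 45% with the Clarius, and calls that 15% gap clinically significant. It states no proportion of discordant pairs.

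Nowhere does the document give an equivalence or non-inferiority margin, a confidence-interval rule, limits of agreement or any other agreement measure. It does not say that a non-significant result will be read as equivalence; it gives no rule for concluding equivalence.

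**The concern.** A test whose null is no difference can show that two machines differ. Failing to reject that null does not show that they agree closely enough. Followed exactly, the plan therefore has no route to its stated conclusion, for detection or for dating.

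Two consequences follow if the gap is filled informally after the data are in.

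- **Detection.** Reading non-significance as equivalence makes the risk of passing an inferior device depend on the discordance between the scans, not on an error rate anyone chose.
- **Dating.** The t-test examines the average difference only. Over- and under-readings cancel, so a near-zero mean is compatible with wide disagreement patient by patient, and a pregnancy is dated one patient at a time.

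The Background and Dissemination sections look ahead to use where radiologist ultrasound is scarce and to studies in remote locations, so an unsupported equivalence claim could travel.

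**Working it through.** **Inputs.** From the Sample Size section: 60% v 45% (d = 0.15), one-sided alpha 0.05 (z = 1.645), power 0.80 (z = 0.842), n = 131 pairs. Assumed, because the protocol gives no value: the discordant proportion ψ and the SD of paired measurement differences.

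**1. The plan's own figure.** If the two scans were independent, ψ = 0.60×0.55 + 0.40×0.45 = 0.51.

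- Unpooled variance: n = (1.645+0.842)² × (0.51−0.0225)/0.0225 = 134.
- Usual McNemar formula: n = [1.645√ψ + 0.842√(ψ−0.0225)]²/0.0225 = 139 at ψ = 0.51, and 131 at ψ = 0.484.

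So 131 is consistent with a test of difference. It was not derived from an equivalence criterion.

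**2. Chance that a true 15-point deficit is non-significant.** Miss = 1 − Φ[(d√n − 1.645√ψ)/√(ψ−d²)], with n = 131 and d = 0.15.

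| ψ | 0.20 | 0.30 | 0.40 | 0.484 | 0.51 |
|---|---|---|---|---|---|
| Miss | 1.0% | 6.1% | 13.5% | 20.0% | 21.9% |

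The 20% at 0.484 is simply the stated 80% power, because that ψ was solved from 131. Independence (0.51) is the upper bound if the scans are not negatively associated. It is unlikely to be reached when one provider usually does both.

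**3. A high-discordance example.** Suppose 38 pairs are seen on the Zonare only and 25 on the Clarius only, so ψ = 63/131 = 0.48. Then z = 13/√63 = 1.64 and one-sided p = 0.051, not significant. The difference is 13/131 = 9.9 points and its upper one-sided 95% limit is 19.8 points (Wald) or 19.7 (score). That result is compatible with a deficit larger than the one the protocol calls clinically significant.

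**4. Dating.** With a true mean difference of zero, a t-test at the 5% level is non-significant 95% of the time whatever the spread. For sac diameter, an assumed SD of paired differences of 2 to 4 mm gives 95% limits of agreement of ±1.96×2 = ±3.9 mm to ±1.96×4 = ±7.8 mm. The Background says "The growth of the MSD is approximately 1 mm per day", so this is about ±4 to ±8 days. It gives no such conversion for crown rump length, so no figure is offered there. The two measures need separate analysis in any case, since "Mean sac diameter becomes less reliable when it exceeds 14 mm or an embryo can be identified", whereas "Crown rump length provides the most accurate estimate of gestational age when the embryo is clearly seen".

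**5. Power of 131 pairs if 15 points became the margin m.** Non-inferiority power = Φ[(m−d)√n/√(ψ−d²) − 1.645]. With d = 0, two-sided equivalence power = 2×(non-inferiority power) − 1. The top ψ here is 0.50, the most that independence allows when the two rates are equal.

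| ψ | 0.20 | 0.30 | 0.40 | 0.484 | 0.50 |
|---|---|---|---|---|---|
| Non-inferiority, d = 0 | 99% | 93% | 86% | 80% | 78% |
| Equivalence, d = 0 | 97% | 86% | 72% | 59% | 57% |
| Non-inferiority, d = 0.05 | 82% | 68% | 57% | 50% | 49% |
| Non-inferiority, d = 0.10 | 37% | 28% | 23% | 21% | 20% |
| Non-inferiority, m = 0.10, d = 0 | 82% | 67% | 57% | 50% | 49% |

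At the protocol's own 60% v 45%, d equals m and power is about 5% at any sample size.

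**6. Exclusions.** Participants with "no evidence of a pregnancy inside or outside of the uterus" leave the comparison, and 131 is not inflated for this. If an assumed 13 or 26 concordant pairs are dropped, ψ becomes ψ×131/118 or ψ×131/105. Non-inferiority power at d = 0 falls to 88% or 81% from ψ = 0.30, and to 72% or 63% from ψ = 0.484.

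**The case against.** The strongest defence is that the Sample Size section already contains a one-sided test and a clinically important difference, which together look like a non-inferiority design. They would be one if the data had to exclude 15 points. But that figure is only the alternative in the power calculation and never reaches the analysis, and dating has no counterpart.

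Several narrower points stand:

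- **Detection harm depends on discordance.** With 16 to 37 discordant pairs (up to about 28% of 131), every non-significant one-sided result also has an upper limit below 15 points. At 37 pairs the largest non-significant split, 23 v 14, gives 14.4 (Wald) or 14.6 (score). In that range the two readings do not conflict. The 38 v 25 example is from the unfavourable end.
- **Sidedness.** One-sidedness is stated for the sample size only. A two-sided analysis would raise the miss rates in step 2.
- **Endpoint.** The 60% and 45% refer to seeing a sac and yolk sac, whereas the planned McNemar outcome is presence of an intrauterine pregnancy. No rates are given for the latter.
- **Dating illustration.** The SDs are assumed, and ±4 to ±8 days is similar in size to the 3 to 8 days the Background quotes for crown rump length accuracy. The illustration shows what the t-test cannot see; it does not show that the Clarius is inaccurate.

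None of these supplies the missing margin or decision rule.

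**Conclusion.** The concern holds and must be fixed. The study's only objective is equivalence, and neither of its two planned tests can support that conclusion. This follows from the text alone and needs no assumption.

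The size of the harm does rest on assumptions. For detection, treating non-significance as equivalence would pass a true 15-point deficit about 1% of the time at discordance 0.20 and 22% at 0.51, given a one-sided 0.05 test and 131 evaluable pairs. For dating there is no protection against individual disagreement of any size. The 131 figure is not shown to be wrong; it answers a different question from the one the protocol asks.

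**What to change.** **Detection.** Before the data are seen, fix and justify a margin: 15 points if the investigators accept it as such, or a smaller one. Report Zonare minus Clarius detection with a confidence interval for paired proportions. Make non-inferiority the main rule (upper one-sided 95% limit below the margin), which matches the one-sided sample size. Claim two-sided equivalence only if the 90% interval lies wholly within plus or minus the margin. Use the same endpoint definition in the sample size and the analysis.

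**Dating.** Report the mean paired difference with its 90% interval against a margin that the investigators fix and justify in advance, plus 95% limits of agreement, separately for sac diameter and crown rump length. Apply the 1 mm per day conversion to sac diameter only.

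**Both.** Keep the McNemar and t-test p-values as descriptive, and state that non-significance is not evidence of equivalence.

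**Cost.** Protocol wording and a little more analysis of data already planned. Restate the power of 131 for the new rule over a range of discordance, true deficits and exclusions. It is reasonable for non-inferiority at 15 points if the machines are truly alike, but falls quickly if the Clarius is worse or the margin tighter. The proportionate response is to state that power openly and limit the claim to what it supports, without enrolling more participants.
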